### **8.3.2 Peripheral Neuropathy**

Signs/symptoms of peripheral neuropathy may include: hypoesthesia, hyperesthesia, paresthesia, discomfort, a burning sensation, neuropathic pain, or weakness.

If peripheral neuropathy is observed, additional serum/plasma samples may be drawn at the time of the event to evaluate drug concentration and ADA, as well as to assess levels of cytokines and/or other markers of inflammation.

Peripheral neuropathy is a known adverse event from MMAE-based ADCs and can be expected to occur with OBI-999. Therefore, specific assessment for signs and symptoms of peripheral neuropathy should be performed at each physical exam. Patients who develop peripheral neuropathy should be followed until resolution in order to define the time to resolution of the neuropathy.

Additionally, non-symptomatic patients will continue to be monitored for possible signs and symptoms of peripheral neuropathy as part of the Safety Follow-Up period.

#### **8.3.2.1 Management of Peripheral Neuropathy**

For new or worsening Grade 2 or 3 peripheral neuropathy, OBI-999 dosing should be held until neuropathy improves to Grade 1 or baseline. OBI-999 dosing may be restarted at a reduced dose (75% of the full dose; see [Table 8-1](#)).

For Grade 4 peripheral neuropathy, OBI-999 should be permanently discontinued.

### **8.4 Study Treatment Assignment**

During Part A, patients were assigned to a dose level in the order of study entry.

During Part B, all patients will receive a dose level of 1.2 mg/kg (capping administered dose to a maximum of 120 mg for 100 kg) of OBI-999.

### **8.5 Treatment Accountability and Compliance**

All drug supplies will be provided by the Sponsor. Administration of study drug will be supervised by study personnel to ensure compliance.

## 8.6 Prior and Concomitant Illnesses and Medications

### 8.6.1 Prior and Concomitant Illnesses

Investigators should document all prior significant illnesses that the patient has experienced prior to screening. Additional illnesses present at the time when informed consent is given and up to the time of first dosing are to be regarded as concomitant illnesses. Illnesses first occurring or detected during the study and/or worsening of a concomitant illness during the study are to be documented as AEs on the eCRF.

### 8.6.2 Prior and Concomitant Medications

All medications and other treatments taken by the patient prior to the start of the study at screening and treatments initiated during the study, must be recorded on the eCRF. The entry must include the dose, regimen, route, indication, and dates of use.

After the baseline visit, medication to treat minor illness(es) are generally permitted, including:

- Use of localized palliative radiation for pre-existing lesions to control pain, at the discretion of the physician.
- Corticosteroids use: topical, inhaled, ophthalmologic, intra-articular, or intranasal corticosteroids; systemic steroids at physiologic doses not to exceed 10 mg/day of prednisone or equivalent. For management of side effects including nausea or infusion reactions, intermittent prophylactic or therapeutic use of glucocorticoids is allowed at doses required for medical therapy administered according to institutional standard of care and at the Investigator's discretion.

### 8.6.3 Prohibited Medications

If there is a clinical indication for the use of one of the following prohibited medications, then discontinuation from the study drug may be required.

- Anti-neoplastic therapy, whether approved or experimental, including but are not limited to: chemotherapy, immunotherapy, surgery, radiotherapy are not allowed with OBI-999. **NOTE:** Use of localized palliative radiation for pre-existing lesions to control pain may be allowed at the discretion of the physician.
- Immunosuppressive therapy (e.g., cyclosporine, rapamycin, tacrolimus, cyclophosphamide, methotrexate, etc.).
- Systemic steroids of >10 mg/day prednisone or equivalent
- Any other concurrent investigational therapy, regardless of indication.
- Strong inhibitors or inducers of CYP3A (see [Appendix 2](#))
- Clinical inhibitors of P-glycoprotein (see [Appendix 3](#))

## **9        Study Procedures**

[Table 9-1](#) outlines the timing of procedures, and assessments to be performed throughout the study.

[Table 9-2](#) and [Table 9-3](#) outline the PK and ADA Sampling Schedules in Part A and Part B, respectively.

### **9.1      Patient Informed Consent**

Prior to performing any study-related procedures, the Investigator (or his/her designated staff member) will obtain written informed consent from the patient. A separate biospecimen consent (pre-screening) for Globo H testing may be utilized in order to ensure that eligibility criterion is met for Part B patients prior to consenting the subject for the remaining eligibility-related procedures. This two-step consent process may streamline the screening process, ensuring timely availability of the Globo H result and avoiding having the patient consent for the remaining procedures until he/she is confirmed to have the requisite Globo H expression for study entry.

### **9.2      Procedures by Study Period**

Assessments and study procedures are to be performed as outlined in the Schedule of Assessments, [Table 9-1](#). The PK and ADA Sampling Schedules are provided in [Table 9-2](#) (Part A) and [Table 9-3](#) (Part B).

The Investigator may at his/her discretion arrange for a patient to have an unscheduled assessment, especially in the case of AEs that require follow-up or an AE considered by the Investigator to be possibly related to the use of study drug. The unscheduled visit page on the eCRF must be completed. Additional visits to follow-up positive ADA may happen after end of study ([Table 9-1](#)).

**Table 9-1 Schedule of Assessments**

Study Procedure	Screening Visit	Treatment Period						EoS / ET	F/U
		Cycle 1					Cycle 2-35		
Cycle (C) #	-								
Cycle # and Day		C1D1	C1D2	C1D4	C1D8	C1D11	C1D15	D1	
Window period (days)	-28 to -1	-1*	±1	±3	±3	±3	±3	±3	±7
Informed consent a	X								
Demographics	X								
Eligibility screening	X	X							
Medical history b	X	X							
Physical examination c	X	X			X*		X	X	X
Height, weight d	X d	X					X	X	
Vital signs e	X	X					X	X	
Ophthalmology examination f	X						Q6wk for the first 6 months, then Q9wk thereafter f		X
ECOG g	X						X	X	
12-lead ECG h	X	X		X g				X	
Pregnancy testing i	X							X	
Tumor biopsy j	X								
Hematology and serum chemistry k	X	X			X		X	Every week for Cycles 2 and 3, then D1 of Cycles 4+	X
Coagulation and urinalysis l	X							D1 of each 21-day cycle l	X
Drug administration m		X						D1 of each 21-day cycle	
Pharmacokinetic sample n			See footnote n						
Immunogenicity (ADA) o		X						See footnote o	X
Radiology evaluations (CT or MRI) p	X							Q6wk for the first 3 months, then Q9wk thereafter	X
Concomitant medications		↔							
Adverse events		↔							→

Abbreviations: ADA = anti-drug antibody; D = Day; C = Cycle; CT = computed tomography; ECG = electrocardiogram; ECOG = Eastern Cooperative Oncology Group; EoS = End of Study; ET = Early Termination; F/U = follow-up; MRI = magnetic resonance imaging; Q6wk = every 6 weeks; Q9wk = every 9 weeks

EoS Visit is the safety follow-up visit, conducted  $28\pm 7$  days after the last OBI-999 dose. ET Visit lab assessments will be conducted for patients discontinuing study treatment, if last available tests are before 2 weeks.

\*The - 1 day window (1 day prior) for C1D1 is for safety laboratory assessments. Blood can be drawn 1 day prior to initiation of study drug infusion on C1D1. Safety laboratory results should be available and reviewed by the Investigator prior to the OBI-999 administration.

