### **6.1.3 Duration of Study**

The study (Parts A and B) will include a screening period (up to 28 days), a treatment period, and a follow-up period.

Patients will continue to receive treatment with OBI-999 until disease progression, unacceptable toxicity, consent withdrawal, or for up to 35 cycles (approximately 2 years), whichever occurs first. Patients will be followed up to the 24-week scheduled response assessment for the purposes of counting objective responses for Simon's two-stage design success criteria.

The safety follow-up visit will be conducted 28 days after the last dose of study treatment.

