p. Radiology (CT or MRI scan) evaluations of tumor response: Performed during screening and during the study every 6 weeks for the first 3 months, and then every 9 weeks until discontinuation of study treatment, disease progression, death, or initiation of further systemic cancer therapy, including radiation therapy, whichever occurs earlier. CT or MRI scan will be performed within 1 week prior to the start of the next cycle. Unscheduled scan can be performed anytime, if needed to confirm disease progression. Radiology assessment for early termination/end of study, should ONLY be performed if  $\geq 9$  weeks have passed from the previous scheduled CT/MRI scan. Same assessment method and same technique should be used on each patient while on study.

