## **12.5 Adverse Events**

### **12.5.1 Adverse Events**

An AE is any symptom, physical sign, syndrome, or disease that either emerges during the study period or worsens during the study, regardless of the suspected cause of the event. All medical and psychiatric conditions (except those related to the indication under study) present at screening will be documented in the medical history eCRF. Changes in these conditions and new symptoms, physical signs, syndromes, or diseases should be noted on the AE eCRF during the rest of the study. Clinically significant laboratory abnormalities should also be recorded as AEs. Surgical procedures that were planned before the patient enrolled in the study are not considered AEs if the conditions were known before study inclusion; the medical condition should be reported in the patient's medical history.

Patients will be instructed to report AEs at each study visit. All AEs are to be followed until resolution or until a stable clinical endpoint is reached.

Each AE is to be documented on the eCRF with reference to date of onset, duration, incidence, severity, relationship to study drug, action taken with study drug, treatment of event, and outcome. Furthermore, each AE is to be classified as being serious or non-serious. Changes in AEs and resolution dates are to be documented on the eCRF.

For the purpose of this study, treatment emergent AEs will be collected starting from the time the patient receives the first dose of study drug (from Cycle 1 Day 1) until 28 days after the last dose of study drug. Follow-up of the AE, even after the date of therapy discontinuation, is required if the AE persists until the event resolves or stabilizes at a level acceptable to the Investigator.

Specific guidelines for classifying AEs by intensity (Grade) and relationship to study drug are given in Table 12-2 and [Table 12-3](#). The severity of AEs will be graded according to the NCI CTCAE version 5.0 (Grades 1 to 5).

When changes in the intensity of an AE occur more frequently than once a day, the maximum intensity for the event should be noted.

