### **12.5.3 Serious Adverse Event Reporting**

An SAE occurring during the study from the first dose of study treatment (Cycle 1 Day 1) to within 28 days of stopping the treatment must be reported to the contracted CRO and will be communicated to the Sponsor. Any such SAE due to any cause, whether or not related to the study drug, must be reported within 24 hours of occurrence or when the Investigator first becomes aware of the event. The Investigator must enter all SAE information into the electronic data capture (EDC) (preferred method), electronic mail (SAE Report Form), dedicated fax line or telephone line (emergency), to the Sponsor/contracted CRO.

If the Investigator contacts the contracted CRO by telephone, then a written report must follow within 24 hours and is to include a full description of the event and sequelae in the format detailed in the SAE reporting form.

The event must also be recorded on the standard AE eCRF. Preliminary reports of SAEs must be followed by detailed descriptions later on, including clear and anonymized photocopies of hospital case reports, consultant reports, autopsy reports, and other documents when requested and applicable. SAE reports must be made whether or not the Investigator considers the event to be related to the investigational drug.

Appropriate remedial measures should be taken to treat the SAE, and the response should be recorded. Clinical, laboratory, and diagnostic measures should be employed as needed in order to determine the etiology of the problem. The Investigator must report all additional follow-up evaluations to the contracted CRO within 10 calendar days. All SAEs will be followed until the Investigator and Sponsor agree the event is satisfactorily resolved or returns to the baseline condition.

Any SAE that is not resolved by the end of the study or upon discontinuation of the patient's participation in the study is to be followed until it either resolves, stabilizes, returns to baseline values (if a baseline value is available), or is shown to not be attributable to the study drug or procedures.

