10.7.1 PRIMARY ENDPOINTS

PART A (DOSE-ESCALATION)

A. AEs/ SAEs and laboratory abnormalities as graded by NCI CTCAE version 5.0*.

Treatment emergent adverse events (TEAEs) are defined as AEs with onset dates on or after the start of study drug until 28 days after the last dose of study drug or if it is present prior to receipt of the study treatment but worsens in severity or increases in frequency on or after the first dose. AEs having both onset and end dates missing will be considered as TEAEs.

TEAEs will be summarized by study part, cohort (by dose level in Part A and by cancer type in Part B), SOC, PT, severity grade, and relationship to treatment. SAEs, deaths, and AEs leading to early treatment discontinuation (collected on Adverse Events eCRF page) will be summarized. The summaries will be sorted by decreasing order of overall incidence of SOCs and decreasing order of overall incidence of PTs within SOCs.

Events reported as “Unrelated” or “Unlikely related” to study drug will be considered as unrelated to the study drug. Events reported as “Possibly related”, “Probably related”, “Definitely related” to study drug or without relationship information will be considered as related to the respective treatment.

Overview summaries of the number and percentages of patients and number of events within the following categories will be provided by study part and by cohort (by dose level in Part A and by cancer type in Part B):

- Any TEAE
- Any TEAE grade ≥ 3
- Any TEAE related to OBI-999
- Any Serious TEAE
- Any Non-Serious TEAE
- Any Serious TEAE related to OBI-999
- Any TEAE leading to death
- Any TEAE leading to discontinuation of OBI-999 (defined as AE with an action taken equals to “Drug Withdrawn”)
- Any Serious TEAE leading to discontinuation of OBI-999 (defined as AE with an action taken equals to “Drug Withdrawn”)
- Any TEAE leading to study discontinuation (defined as AE flagged as Grade 4 infusion reactions and OBI-999 related toxicity, or intercurrent illness in the “End of Study” eCRF

page)

- Any Serious TEAE leading to study discontinuation (defined as AE flagged as Grade 4 infusion reactions and OBI-999 related toxicity, or intercurrent illness in the “End of Study” eCRF page)

Tables by SOC and PT will be displayed for following AEs. Only those AEs marked with * will be analyzed in the aCSR as per sponsor decision.

- TEAEs*
- TEAEs grade ≥ 3 *
- TEAEs related to OBI-999*
- Serious TEAEs*
- Non-Serious TEAEs

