15. APPENDIX I. SCHEDULE OF ASSESSMENTS**TABLE 14-1 SCHEDULE OF ASSESSMENTS**

Study Procedure	Screening Visit	Treatment Period						EoS / ET	F/U
		Cycle 1							
Cycle (C) #	-	Cycle 1						Cycle 2-35	
Cycle # and Day		C1D1	C1D2	C1D4	C1D8	C1D11	C1D15	D1	
Window period (days)	-28 to -1	-1 [*]	±1	±3	±3	±3	±3	±3	±7
Informed consent ^a	X								
Demographics	X								
Eligibility screening	X	X							
Medical history ^b	X	X							
Physical examination ^c	X	X			X*			X	X
Height, weight ^d	X ^d	X						X	X
Vital signs ^e	X	X						X	X
Ophthalmology examination ^f	X							Q6wk for the first 6 months, then Q9wk thereafter ^f	X
ECOG ^g	X							X	X
12-lead ECG ^h	X	X		X ^g					X
Pregnancy testing ⁱ	X								X
Tumor biopsy ⁱ	X								
Hematology and serum chemistry ^k	X	X			X		X	Every week for Cycles 2 and 3, then D1 of Cycles 4+	X
Coagulation and urinalysis ^l	X							D1 of each 21-day cycle ^l	X
Drug administration ^m		X						D1 of each 21-day cycle	
Pharmacokinetic								See footnote n	

sample ⁿ								See footnote o	X	X ⁿ
Immunogenicity (ADA) ^p		X								
Radiology evaluations (CT or MRI) ^p	X							Q6wk for the first 3 months, then Q9wk thereafter	X	
Concomitant medications		↔							↔	
Adverse events			↔							

Abbreviations: ADA = anti-drug antibody; D = Day; C = Cycle; CT = computed tomography; ECG = electrocardiogram; ECOG = Eastern Cooperative Oncology Group; EoS = End of Study; ET = Early Termination; F/U = follow-up; MRI = magnetic resonance imaging; Q6wk = every 6 weeks; Q9wk = every 9 weeks

EoS Visit is the safety follow-up visit, conducted 28 ± 7 days after the last OBI-999 dose. ET Visit lab assessments will be conducted for patients discontinuing study treatment, if last available tests are before 2 weeks.

*The - 1 day window (1 day prior) for C1D1 is for safety laboratory assessments. Blood can be drawn 1 day prior to initiation of study drug infusion on C1D1. Safety laboratory results should be available and reviewed by the Investigator prior to the OBI-999 administration.

Footnotes:

- a. Informed consent to be obtained before any other study procedures are performed.
- b. Medical history, including previous cancer therapies, cancer history, and past and ongoing concomitant illnesses which are relevant to the disease under study.

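### The safety follow-up visit may be held from Day 21 after the last dose while adverse event windows run to Day 28, leaving up to 7 days with no scheduled contact to elicit new events

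*Protocol*

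**What the plan says.** **Visit timing.** The notes to Protocol Table 9-1 state that "EoS Visit is the safety follow-up visit, conducted" 28±7 days after the last dose. SAP Appendix I repeats this: "EoS Visit is the safety follow-up visit, conducted 28 ± 7 days after the last OBI-999 dose". The body text gives the same visit without a tolerance. Protocol section 6.1.3 says "The safety follow-up visit will be conducted 28 days after the last dose of study treatment", and the protocol synopsis (Treatment Duration) and SAP section 5.1.4 agree with it.

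**Event windows.** Protocol section 12.5.1 collects treatment-emergent AEs ("from Cycle 1 Day 1) until 28 days after the last dose of study drug"). Section 12.5.3 sets the SAE period from the first dose "to within 28 days of stopping the treatment must be reported". SAP section 10.7.1 counts AEs with onset "on or after the start of study drug until 28 days after the last dose of study drug". SAP section 10.6.3 applies the same 28-day limit to concomitant medications.

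**How events are found.** Under Protocol section 12.5.1, patients are told to report AEs at study visits. The text of neither document schedules a telephone call after the safety follow-up visit. The only later dated contact is an ADA sample 4 months afterwards, for patients with persistent antibodies (Table 9-1, footnote o).

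**Early termination.** Protocol section 7.3 asks patients who withdraw prematurely to attend an early-termination visit if possible, but does not tie it to a day after the last dose. In Table 9-1 that visit shares a column with the end-of-study visit.

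**The concern.** The visit that prompts patients for late events may come up to a week before the period it serves has ended. A site can comply fully with Table 9-1 and have no further scheduled opportunity to ask about new events in the remaining days, yet the patient is reported under the same 28-day definition as one seen on Day 28 or later. Observation time then differs between patients according to the visit date.

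Safety and tolerability is the first primary objective, and AEs/SAEs are an endpoint kept for the abbreviated report in both parts (SAP section 8). SAP section 11 reduces the section 10.8.2 laboratory data, vital signs and ECG to listings, and drops ECOG, physical examination and ophthalmology. The TEAE tables therefore carry most of the safety summary, including the table of TEAEs leading to death. The risk is some under-ascertainment of late-onset events, mainly non-serious ones.

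**Working it through.** No sample-size or power figure is involved; this is day arithmetic on the stated windows.

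**Inputs**
- Visit target 28 days, tolerance ±7 days (Protocol Table 9-1; SAP Table 14-1).
- End of AE, SAE and TEAE windows: Day 28 after the last dose (Protocol 12.5.1 and 12.5.3; SAP 10.7.1).
- Cycle length 21 days (Protocol 8.2.2).

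**Step 1: compliant visit days.** Earliest = 28 − 7 = Day 21. Latest = 28 + 7 = Day 35.

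**Step 2: days without scheduled elicitation.** For a last visit on day *d*, gap = max(0, 28 − *d*).

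| Last visit | Gap (days) | Share of the 28 days |
|---|---|---|
| Day 21 | 7 (Days 22 to 28) | 7/28 = 25% |
| Day 24 | 4 | 4/28 = 14% |
| Day 27 | 1 | 1/28 = 4% |
| Day 28 to 35 | 0 | 0% |

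**Step 3: share of a short treatment course (illustration).** For a patient who receives two doses 21 days apart, the TEAE window is 21 + 28 = 49 days. A Day 21 visit leaves 7/49 = 14% of it. The two-dose course is assumed for illustration.

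**Step 4: could a visit plausibly fall near Day 21?** Footnote p of Table 9-1 says "CT or MRI scan will be performed within 1 week prior to the start of the next cycle". With 21-day cycles, that puts such a scan about 14 to 21 days after the preceding dose, and the next planned attendance at about Day 21. An early visit is therefore possible. Protocol section 10 allows ±7 days for scans, and neither document says when the final visit is held after progression is found, so no frequency follows.

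**Step 5: does another provision cover the remaining days?**
- Unscheduled assessments (Protocol 9.2) are at the investigator's discretion.
- Following ongoing AEs to resolution or stability (12.5.1, 7.3) does not detect new onsets.
- The 24-hour SAE rule (12.5.3) applies without a visit, but depends on the site learning of the event.
- Neuropathy monitoring of non-symptomatic patients in the safety follow-up period (8.3.2) has no date of its own.

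Each reduces the gap. None schedules a contact between an early visit and Day 28.

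**The case against.** The strongest reply is that Day 28 is the stated target and ±7 days is an ordinary scheduling tolerance. The duty to collect AEs does not end at the visit: section 12.5.1 runs to Day 28 whatever the visit date, and SAEs are reportable on awareness. An AE that leads to discontinuation is followed until it resolves or stabilises. DLTs are assessed over the first 21 days of treatment and the RP2D is already set, so neither is affected. The summaries are descriptive and single-arm, so no between-arm comparison can be biased. Editing the schedule cannot recover contacts in a study that has stopped.

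Most of this stands and limits the point, but it leaves new-onset events after an early visit without a scheduled prompt. Several stronger readings are tempting and are not supported:
- **That the remaining days are unobserved.** They lack a scheduled contact; reporting duties continue.
- **That closing a patient at about Day 21 is the typical case.** The scan timing makes it possible; no text says it is usual.
- **That an early-termination visit replaces the safety follow-up visit, making the gap longer than 7 days.** A shared table column does not establish this, and sections 6.1.3 and 7.3 do not settle it. If a site took it that way, the gap could exceed 7 days.
- **That the follow-up column of Table 9-1 serves only the ADA sample.** Its marks cannot be read reliably in the copy available, so nothing here rests on it.

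**Conclusion.** The mismatch is real and modest. A compliant visit on Days 21 to 27 leaves 1 to 7 days of the plan's own 28-day window without a scheduled visit or call to elicit new AEs. The figures of 25% of the post-dose window, and 14% of a two-dose course, are maxima at the edge of the tolerance. They measure days without scheduled elicitation and should not be read as a proportion of events lost.

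The conclusion assumes that no separate document, such as a site manual, requires a later contact. The documents give neither the distribution of actual visit days nor the rate of events in Days 22 to 28, so the number of missed events cannot be estimated. The safety data are not invalidated. The point still goes beyond missing detail, because the schedule does not match the definition used for a primary safety objective and the correction is cheap. The sponsor should also reconcile the 28-day body text with the 28±7-day tables and state how the early-termination visit relates to the safety follow-up visit.

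**What to change.** **Schedule (Protocol Table 9-1 and SAP Table 14-1).** Change the safety follow-up window to 28 (+7) days after the last dose. Add that if the last visit, including an early-termination visit, falls before Day 28, AEs, SAEs and concomitant medications are collected by telephone on Days 28 to 35. State whether an early-termination visit replaces the safety follow-up visit, and carry the same window into the synopsis, Protocol 6.1.3 and SAP 5.1.4. The 28-day limit on TEAEs stays as it is.

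**Abbreviated report.** Since the sponsor stopped the study on 10 November 2023 (SAP section 3), a schedule change cannot recover past contacts. Beside the TEAE tables, report by part and cohort the day of last AE contact relative to the last dose, and the number of patients last contacted before Day 28. This shows whether the gap arose and for how many patients.

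**Cost.** A short amendment, a narrower visit window (8 compliant days, Days 28 to 35, instead of 15, Days 21 to 35), one telephone call for some patients, and one small addition to the report. No dose or treatment rule changes.
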